### 9.1 Serious Adverse Events

A SAE is defined as any AE that:

- Results in death (ie, the AE actually causes or leads to death).
- Is life threatening (ie, the AE, in the view of the investigator, places the subject at immediate risk of death. It does not include an AE that, had it occurred in a more severe form, might have caused death).
- Requires or prolongs in-patient hospitalization.
- Results in persistent or significant disability or incapacity (ie, the AE results in substantial disruption of the subject’s ability to conduct normal life functions).
- Results in a congenital anomaly or birth defect in a neonate/infant born to a mother exposed to IP prior to conception or during pregnancy.

- Is considered a significant medical event by the investigator based on medical judgment (eg, may jeopardize the subject or require medical or surgical intervention to prevent 1 of the outcomes listed above).

The reporting period for SAEs is the period from administration of the first dose of study drug through 30 days after the last administration of study drug. SAEs reported to the investigator outside of this reporting period will be reported to Olema Pharmaceuticals or its designee if, in good medical judgment, the event has any bearing on the study data. SAEs must be followed by the investigator until resolution, or until the subject is lost to follow-up, even if this extends beyond the study-reporting period. Resolution of an SAE is defined as the return to baseline status or stabilization of the condition with the expectation that it will remain chronic.

Any SAE, whether or not considered related to study drug, will be reported immediately (within 24 hours of learning of the event) to Olema Pharmaceuticals or its designee using the electronic data capture system. If the electronic data system is unavailable, the SAE may be reported by fax using the study-specific SAE Report Form, but should be entered in the electronic data capture system as soon as it becomes available. In addition to the outcome of the SAE, any medication or other therapeutic measures used to treat the event will be recorded in the appropriate eCRF page(s). Investigators or designees should not wait to collect additional information that fully documents the event before notifying Olema Pharmaceuticals or its designee of an SAE. Olema Pharmaceuticals may be required to report certain SAEs to regulatory authorities within 7 calendar days of being notified about the event; therefore, it is important that investigators or designees submit additional information requested by Olema Pharmaceuticals or its designee as soon as it becomes available.

Reporting of SAEs to the IRB/EC will be done in compliance with the standard operating procedures and policies of the IRB/EC and with applicable regulatory requirements. Adequate documentation must be obtained by Olema Pharmaceuticals or its designee showing that the IRB/EC was properly and promptly notified as required.

The SAE form should be faxed to [REDACTED]

The investigator is encouraged to discuss with the Medical Monitor any AEs for which the issue of seriousness is unclear or questioned. Contact information for the Medical Monitor is as follows:

[REDACTED]

## 9.2 Adverse Events of Special Interest

Adverse events of special interest (AESI) are required to be reported by the investigator to the sponsor within 24 hours after learning of the event regardless of the causality to study drug. The most appropriate diagnosis or if a diagnosis cannot be established, the abnormal laboratory values should be recorded on the Adverse Event eCRF and reported to the sponsor, either as an SAE or as an AESI.

AESI for OP-1250 are:

- Neutropenia Grade 4.
- Decreased neutrophils Grade 4.

## 9.3 Pregnancies

Although pregnancy and lactation are not considered AEs, it is the responsibility of Investigators or their designees to report any pregnancy or lactation in a subject (spontaneously reported to them) that occurs during the study or within 90 days following cessation of treatment or, if the subject initiates new anticancer therapy, 30 days following cessation of treatment, whichever is earlier. All subjects who become pregnant must be followed to the completion/termination of the pregnancy. Pregnancy outcomes of spontaneous abortion, missed abortion, benign hydatidiform mole, blighted ovum, fetal death, intrauterine death, miscarriage, and stillbirth must be reported as SAEs (Important Medical Events). If the pregnancy continues to term, the outcome (health of infant) must also be reported.

Such events must be reported within 24 hours to the Sponsor either by electronic media or paper. Sponsor Contact information can be found in the Study Manual.

Please refer to the Study Manual for further details on the pregnancy reporting procedure and associated report form.

## 10 STUDY PROCEDURES, EVALUATIONS, AND SCHEDULE

### 10.1 Screening and Baseline Assessments

At the start of the screening period, prospective study subjects will be fully informed about the nature of the study and possible risks. Subjects must read and sign the informed consent form (ICF) after the investigator has answered all questions to the subject's satisfaction.

After obtaining informed consent, subjects will undergo screening procedures to confirm eligibility to participate in the study. Screening procedures must be performed within 28 days prior to initiating study therapy. The investigator must evaluate the subject's medical history and the results of all screening assessments to determine study eligibility before the subject is enrolled.

The following evaluations and procedures will be performed within 28 days prior to the first study drug administration (C1D1):

- Signed informed consent.
- Medical history, including demographics and prior cancer therapy (see [Section 10.2.1](#)).
- Complete physical examination (see [Section 10.2.2](#)); vital sign measurements, including height and weight (see [Section 10.2.4](#)); and ECOG PS (see [Section 10.2.3](#)).
- 12-lead ECG (see [Section 10.2.5](#)).
- Prior and concomitant medication and therapies (see [Section 10.2.8](#)).
- Laboratory assessments (hematology, chemistry, coagulation, fasting serum lipid profile, urinalysis, serum pregnancy testing, [REDACTED]) (see [Section 10.2.6](#)). Hematology and chemistry tests will be done within 3 days prior to the C1D1 visit and results checked against eligibility criteria prior to dosing at Cycle 1. When noted as "CBC only," all hematology tests are to be performed.
- Pregnancy test (see [Section 10.2.6.6](#)).
- Radiological assessments (see [Section 10.3.1](#)).
- Tumor measurement (see [Section 10.3.2](#)).
- [REDACTED]

If the subject meets all inclusion/exclusion criteria after the Screening visit(s), the site will follow the procedures described in [Section 8.6](#) for subject enrollment.

### 10.2 General Eligibility and Safety Assessments

#### 10.2.1 Medical History and Demographics

The investigator or designee will obtain a detailed medical history, including previous cancer history, by interviewing the subject during Screening. The medical history should include types of treatment for adjuvant therapy and detailed history for the treatment of metastatic disease including types of therapy, dates and best response to therapy. Medical history should also include current and past illnesses and conditions; current symptoms of any active medical

condition; surgeries and procedures; allergies; and social history (eg, smoking, alcohol, illegal substances).

Demographic information, such as the subject's age, ethnicity, and race will be collected by interview with the subject at Screening.

#### **10.2.2 Physical Examination**

A complete physical examination will be performed at Screening and during the EOT visit. Symptom directed physical examination will be performed at every visit, with exception C1D2 where no physical examination is required or if there is a laboratory only visit.

#### **10.2.3 ECOG Performance Status**

The ECOG Performance Status will be assessed as described in [Appendix A](#).

#### **10.2.4 Vital Signs, Height, and Weight**

Vital signs, including blood pressure, pulse rate, respiration rate, and temperature, and weight will be measured. Height will be measured at Screening (baseline) only.

#### **10.2.5 Electrocardiogram**

Triplicate ECGs should be performed after the subject has rested quietly for at least 10 minutes in a supine position. ECGs will be performed in triplicate with a 10-second rhythm strip. When time-matched with a PK sample collection, the ECG should be obtained first. ECGs should be obtained before the assessment of blood pressure and other vital signs.

In some cases, it may be appropriate to repeat abnormal ECGs to rule out improper lead placement as contributing to the ECG abnormality. It is important that leads are placed in the same positions each time in order to achieve precise ECG recordings. If a machine read corrected QT value is prolonged, repeat measurements may not be necessary if a qualified physician's interpretation determines that the QTc values are in the acceptable range. It is preferable that the ECG machine provided for the study is used as it has capacity to calculate the standard intervals automatically.

At each time point, subjects will have 3 consecutive 12-lead ECGs performed 2 to 5 minutes apart to determine mean QTc. If the mean QTcF is prolonged ( $>500$  msec, ie, NCI-CTCAE Grade  $\geq 3$ ), then the ECGs should be re-evaluated by a qualified person at the site for confirmation as soon as the finding is made, including verification that the machine reading is accurate. If manual reading verifies a QTcF of  $>500$  msec, immediate correction for reversible causes (including electrolyte abnormalities, hypoxia and concomitant medications for drugs with the potential to prolong the QTcF interval) should be performed and the Medical Monitor notified.

In addition, repeat ECGs should be performed hourly for at least 3 hours until the QTcF interval falls below 501 msec. If QTcF interval reverts to less than 501 msec, and in the judgment of the investigator or designee and sponsor is determined to be due to cause(s) other than IP, treatment may be continued with regular ECG monitoring. If, in that timeframe, the QTcF rises above 500 msec the IP will be held until the QTcF decreases to 500 msec. Subjects will then restart the IP at the next lowest dose level. If the QTcF has still not

decreased to 500 msec after 2 weeks, or if at any time a subject has a QTcF >515 msec or becomes symptomatic, the subject will be removed from the study. Additional triplicate ECGs may be performed as clinically indicated.

Prior to concluding that an episode of prolongation of the QTcF is due to IP, thorough consideration should be given to potential precipitating factors (eg. change in subject clinical condition, effect of concurrent medication, electrolyte disturbance) and possible evaluation by specialist.

In addition to the planned ECG schedule, an unscheduled ECG should be collected pre-dose as soon as possible after a SAE, and if OP-1250 is dose reduced, pre-dose at the next clinic visit (at least a week after the subject has taken OP-1250 at a reduced dose).

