#### **8.10 Dose Modification for Phase I and Phase II**

All AEs should be assessed according to the NCI-CTCAE, v 5.0. In the event of multiple toxicities, dose delays and modifications should occur in accordance with the highest grade AEs observed.

Institutional guidelines should be followed in the event of hypersensitivity reaction.

Subjects who experience a DLT or any of the following AEs in Cycle 2 and beyond will have study drug treatment interrupted. Dose modification will be allowed as per [Table 8](#). Modified dose levels are shown in [Table 9](#).

Dose Modification Guidelines for Intermediate Doses are presented in [Table 10](#). The first dose reduction will be approximately 20% to 30%, the second dose reduction is

approximately 40% to 50%, and the third dose reduction is approximately 70% to 80%. Dose reductions below 15 mg daily are not allowed.

Dose modifications will only be made for TEAEs that are not clearly due to disease progression or extraneous causes.

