**Table 8: Dose Modification or Treatment Delay for OP-1250-Related Treatment-Emergent Adverse Events**

Worst toxicity NCI-CTCAE, v5.0 a Grade (v5.0)	Recommended dose modifications for OP-1250
Blood	
Febrile Neutropenia Grade 3	
 
Hold OP-1250 until ANC is <math>\geq 1.0 \times 10^9/\text{L}</math> or baseline. If treatment delay is <math>\leq 14</math> days, restart at 1 dose level lower.
 
If treatment delay is <math>> 14</math> days, discontinue treatment.
 

Febrile Neutropenia Grade 4	
 
Discontinue treatment.
 

Investigations	
Neutropenia (ANC/neutrophils decreased)	
Grade 3 (ANC $< 1.0\text{--}0.5 \times 10^9/\text{L}$ )	
 
Hold OP-1250 until ANC is <math>\geq 1.0 \times 10^9/\text{L}</math> or baseline. If treatment delay is <math>\leq 7</math> days, restart at same dose.
 
If treatment delay is <math>> 7</math> but <math>\leq 21</math> days, restart 1 dose level lower.
 
If treatment delay is <math>> 21</math> days, discontinue treatment.
 

Grade 4 (ANC $< 0.5 \times 10^9/\text{L}$ )	
 
Hold OP-1250 until ANC is <math>\geq 1.0 \times 10^9/\text{L}</math> or baseline. If treatment delay is <math>\leq 7</math> days, restart 1 dose level lower.
 
If treatment delay is <math>> 7</math> days, discontinue treatment.
 

Thrombocytopenia (platelet count decreased)	
Grade 3 (Platelets $< 25\text{--}50 \times 10^9/\text{L}$ ) without bleeding	
 
Hold OP-1250 until platelet count is <math>\geq 75 \times 10^9/\text{L}</math>. If treatment delay is <math>\leq 7</math> days, restart at same dose.
 
If treatment delay is <math>> 7</math> but <math>\leq 21</math> days, restart 1 dose level lower.
 
If treatment delay is <math>> 21</math> days, omit dose and discontinue treatment.
 

Grade 4 (Platelets $< 25 \times 10^9/\text{L}$ ) or Grade 3 with bleeding	
 
Hold OP-1250 until platelet count is <math>\geq 75 \times 10^9/\text{L}</math>. If treatment delay is <math>\leq 7</math> days, restart 1 dose level lower.
 
If treatment delay is <math>> 7</math> days, discontinue treatment.
 

Renal	
Serum creatinine	

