Grade 2 Sinus bradycardia	
 
Hold OP-1250 until resolution to ≤ Grade 1 or baseline and restart 1 dose level lower.
 
If findings recur on 1 dose level lower, hold until resolves to ≤ Grade 1 or baseline and restart at 2 dose levels lower than original dose.
 
If findings recur on 1 dose level lower, hold until resolves to ≤ Grade 1 or baseline and restart at 3 dose levels lower than original dose.
 
If findings recur, discontinue treatment.
 

Grade ≥ 3 Sinus bradycardia	
 
Discontinue treatment.
 

Grade 3 QTc prolongation	
 
Hold OP-1250; address any serum electrolyte abnormalities.
 
Upon resolution of QTcF to ≤ 500 msec, resume OP-1250 at 1 dose level lower.
 
If findings recur, discontinue treatment.
 

Grade 4 QTc prolongation	
 
Discontinue treatment.
 

Worst toxicity NCI-CTCAE, v5.0 a Grade (v5.0)	Recommended dose modifications for OP-1250
Eye Toxicity	
Grade 2 without changes in visual acuity	
 
• Hold OP-1250, contact Medical Monitor, and have ophthalmologist examination. If no concerning findings suggestive of drug effect and resolved to a <math>\leq</math> Grade 1 restart at 1 dose level lower.
 
• If it recurs, hold OP-1250 and contact Medical Monitor. If resolved to a <math>\leq</math> Grade 1, restart at 2 dose levels lower than original dose.
 
• If it recurs again, hold OP-1250 and contact Medical Monitor. If resolved to a <math>\leq</math> Grade 1, restart at 3 dose levels lower than original dose.
 

Grade 2 with changes in visual acuity Grade 3 or 4	
 
• Discontinue treatment.
 

Neurologic Toxicity	
Grade 2 Headache	
 
• If AE occurs that is not relieved with supportive care for 7 days the investigator or designee can reduce 1 dose level.
 
• If AE occurs that is not relieved with supportive care for 7 days the investigator or designee can reduce 1 additional dose level.
 
• If AE occurs that is not relieved with supportive care for 7 days the investigator or designee can reduce 1 additional dose level.
 

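### Table 8's Grade 3 QTc row omits the stopping limits in Section 10.2.5, so a site using Table 8 alone could re-dose a subject whom 10.2.5 removes

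*Protocol*

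**What the plan says.** Section 10.2.5 applies when a manual reading confirms QTcF above 500 msec, which it equates with Grade 3 or higher. Reversible causes are corrected, the Medical Monitor is notified and ECGs are repeated hourly. If QTcF drops below 501 msec and the cause is judged not to be the drug, "treatment may be continued with regular ECG monitoring". If QTcF rises above 500 msec within a timeframe that the text does not define, drug is held until QTcF is back to 500 msec and then restarted at the next lowest dose level. If QTcF has not "decreased to 500 msec after 2 weeks, or if at any time a subject has a QTcF >515 msec or becomes symptomatic", then "the subject will be removed from the study".

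Table 8 is titled "Dose Modification or Treatment Delay for OP-1250-Related Treatment-Emergent Adverse Events". Its Grade 3 QTc row says to hold drug, correct electrolytes, and: "Upon resolution of QTcF to ≤ 500 msec, resume OP-1250 at 1 dose level lower". It adds "If findings recur, discontinue treatment". Grade 4 QTc prolongation means discontinuation.

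Section 8.10 states "Dose modification will be allowed as per" Table 8. Section 8.3.3 describes unacceptable toxicity by reference to Table 8, and Section 8.11 ties stopping for an adverse event to the same table. None of these cites 10.2.5, and 10.2.5 does not cite Table 8.

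On dose steps, Section 8.10 says "the third dose reduction is approximately 70% to 80%. Dose reductions below 15 mg daily are not allowed"; the synopsis repeats the percentage. Table 10 lists exact doses, with 120 mg reduced to 90, 75 and then 45 mg.

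**The concern.** The stopping limits for a cardiac safety event sit in the ECG procedures section, while the table that the protocol tells sites to use for dosing decisions lacks them. Table 8 sets 7-, 14- or 21-day limits in its neutropenia, febrile neutropenia and platelet rows, so a QTc row without a limit can easily be read as having none.

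A hold longer than 2 weeks is plausible. Sections 6.2 and 6.7 report that in animals the long half-life kept exposure going through the whole 28-day treatment-free recovery period, and Table 11 lists the drug's QT-prolonging property as unknown.

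At stake are whether a subject is re-exposed after prolonged or marked QTc prolongation, and how the case is reported. SAP 9.1 counts treatment discontinuation and study discontinuation separately, each with its primary reason. SAP 13.2 tabulates adverse events leading to discontinuation, dose reduction and withheld drug. The same event could enter different rows depending on which section the site followed.

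**Working it through.** **The two texts side by side, for a drug-related Grade 3 event**

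| Course of the event | Table 8 | Section 10.2.5 | Result |
|---|---|---|---|
| Never above 515 msec, no symptoms, back to 500 msec within 2 weeks | Resume one level lower | Restart at next lowest level | Agree |
| Never above 515 msec, no symptoms, back to 500 msec after more than 2 weeks | Resume one level lower, no time limit | Remove, if the 2-week limit covers drug-related episodes | Differ |
| Above 515 msec at some time, then back to 500 msec | Resume one level lower, if still Grade 3 | Remove | Differ |
| Symptoms, then back to 500 msec | Resume one level lower, if still Grade 3 | Remove | Differ |
| Recurrence on the lower dose | Discontinue | No separate rule | Gap, not a conflict |

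The qualifier about Grade 3 in rows three and four is needed because the documents give no boundary, in msec or otherwise, between Grade 3 and Grade 4. An event classed as Grade 4 is stopped under Table 8 as well.

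**Worked case.** Starting dose 120 mg (the RP2D, Section 8.8.4); drug-related QTcF 505 msec, no symptoms, back to 500 msec on day 21. Since 505 is below 515 and 21 days exceeds 14, only the 2-week limit is in play. Table 8 with Table 10: resume at 90 mg. Section 10.2.5: removal.

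**How large a QTcF change is needed.** Inclusion criterion 14 requires QTcF below 470 msec (females) or below 450 msec (males).
- To exceed 500 msec: a rise of more than 500 − 470 = 30 msec, or 500 − 450 = 50 msec.
- To exceed 515 msec: more than 515 − 470 = 45 msec, or 515 − 450 = 65 msec.

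The documents report no number of such events, so no rate can be computed.

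**Stated percentages against Table 10.** Reduction = 1 − (reduced dose ÷ starting dose).
- 120 mg, third step: 1 − 45/120 = 62.5%, against a stated figure of about 70% to 80%.
- 60 mg, third step: 1 − 15/60 = 75.0%, which fits.

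**The case against.** The strongest reply is that Table 8 is silent rather than contrary. On the core action the two texts agree, and a site complies with both by applying the stricter limit. Table 8's column is headed as recommended modifications, whereas 10.2.5 is worded as mandatory, and a recommendation that is silent on time does not naturally override a specific stop. The Medical Monitor also hears of every verified case. All of this stands. A reader might infer that the two texts flatly contradict each other and cannot both be followed; the documents do not support that.

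A second reply is that in 10.2.5 the hold and 2-week sentences come directly after the provision for causes other than the drug, and refer back to its timeframe. On that reading they govern only those continued episodes, and Table 8 governs drug-related ones. The wording does leave this open. But the reading would give drug-related prolongation the laxer rule, which is unlikely to be intended, and the limit of 515 msec or symptoms applies at any time. The ambiguity is itself a reason to amend.

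On the percentages, a reader might infer that Table 10's doses are wrong. They are not shown to be. The prose says approximately and the table's exact doses can be followed as they stand. Capsules come in 15 and 60 mg, so from 90 mg no 15 mg step lands in the band (30 mg is a 66.7% reduction, 15 mg is 83.3%). The 75 mg row gives 1 − 30/75 = 60.0%, but Section 8.8.4 names only 60 and 120 mg as Part B doses and 120 mg as the RP2D. What remains is a mismatch between prose and table at 120 mg.

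**Conclusion.** The concern holds as an omission in Table 8, not as a contradiction between rules. For drug-related Grade 3 QTc events, a site that follows the table to which Sections 8.3.3, 8.10 and 8.11 direct it could re-dose a subject whom 10.2.5 removes. Nothing in either text says that the stricter rule governs.

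The conclusion on the 2-week limit assumes that the limit covers drug-related episodes, which 10.2.5 leaves unclear. The conclusion on 515 msec and symptoms assumes that the event is still graded 3. The difference in 10.2.5 between leaving the study and stopping treatment may be loose wording, but the SAP counts the two separately, so it should be settled.

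The practical size is small: few subjects are likely to be affected, and the reporting effect is limited to which rows of descriptive safety and disposition tables they enter. It is worth fixing because it concerns a cardiac stopping rule and the limits already exist in the protocol. The 62.5% at the RP2D against about 70% to 80% is a minor editorial point.

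**What to change.** In the next protocol amendment:

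1. **Table 8, Grade 3 QTc row.** Keep the hold and the electrolyte correction, then: *Resume 1 dose level lower only if QTcF is ≤ 500 msec within 2 weeks, never exceeded 515 msec and the subject is asymptomatic; otherwise discontinue treatment. Discontinue treatment on any recurrence.*
2. **Cross-references.** Cite 10.2.5 from Section 8.10 and the Table 8 row, and cite Table 8 from 10.2.5, including for recurrence.
3. **Section 10.2.5.** State that the limits apply to drug-related episodes. Keep the provision for episodes judged due to other causes. State whether removal means discontinuing treatment or leaving the study.
4. **Optional.** Delete the reduction percentages from Section 8.10 and the synopsis and cite Table 10 instead. No dose changes.

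The cost is wording only. Every limit is already in the protocol, and no visits, procedures or subjects are added.
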